6.2. Secondary Analysis

6.2.1. CSF Neurotransmitter Analysis

A summary table of descriptive statistics of the observed values, change from baseline and percentage change from baseline will be presented for 5-HIAA, HVA and 3-OMD by time point. A listing for 5-HIAA, HVA and 3-OMD will be provided.

6.2.2. PET

The expression and activity of the AADC enzyme in the putamen will be assessed through PET imaging using ¹⁸F-DOPA.

A summary table of descriptive statistics will be presented for the observed values and changes from baseline for the mean intensity, specific uptake, max standardized uptake and specific putaminal uptake. Percent change from baseline will be summarized for MAX specific putaminal uptake and specific putaminal uptake. One-sample t-test will be performed for change from baseline for variables in specific putaminal uptake to test whether change and percent change from baseline are statistically significantly different from 0.

A listing of the visual assessment of striatal FDOPA uptake, visual status, visual comments as well as general comments for caudate, putamen and occipital cortex will be provided. Also, mean intensity, specific uptake, max standardized uptake values, and specific uptake values will be presented for putamen and caudate.

6.2.3. Motor Milestones

Motor skills and development milestones will be assessed using PDMS-2. The PDMS-2 instrument will be administered by a qualified physiotherapist. Each skill item is assessed as a simple, 3-level scoring as a consistent way of describing the child's achievement of a particular motor skill, as listed below:

0 = the skill is not met

1 = the skill is emerging and shows a clear resemblance to mastery of the skill item

2 = the child is mastering the motor skill

Motor milestones are achieved in sequential order. Besides the key milestones listed in the protocol, intermittent milestones and more advanced milestones will be assessed. Each motor milestone based on individual item of PDMS-2 are displayed in Table 2. If subjects achieved more advanced milestones than listed, those milestones will also be summarized.

Table 2: Motor Milestones

Normal Age of Achievement	Analytical Term	PDMS-2 Reference (Position and subcategory)	PDMS-2 Description
3 months	Partial head control	Stationary 5	Aligning head (grasp child's hands and pull up to a sitting position, observe head alignment and position at end of cycle)
6 months	Full head control	Stationary 10	Aligning head (sitting, supported with pillows around hips)
6 months	Sitting with assistance	Stationary 11	Sitting (maintain for 8 seconds for score of "2")
10-11 months	Sitting unassisted	Stationary 14	Sitting (unsupported)
10 months	Standing with support	Locomotion 28	Stepping (supported)
11 months	Standing away from support	Locomotion 31	Standing (unsupported)
12 months	Walking with assistance	Locomotion 34	Walking (supported)
12 months	Walking to a toy	Locomotion 35	Walking (unsupported)
15-16 months	Walking up stairs with support	Locomotion 40	Walking up stairs (standing, facing flight of stairs, close to railing or wall)
17-18 months	Walking backward using normal stride	Locomotion 44	Walking backward
21-22 months	Walking on a taped line	Locomotion 48	Walking line

In assessing motor milestones achievement, if the PDMS-2 score for the question used to define a milestone achievement is 1, the milestone is considered "Emerging"; if the score for that question is 2, the milestone achievement is considered "Mastery". In the summary table, stages of milestone achievement used are:

- Emerging (PDMS-2 score =1 for the item assessed)
- Emerging and Mastery (PDMS-2 score=1 or 2 for the item assessed)
- Mastery (PDMS-2 score=2 for the item assessed).

The cumulative number of subjects achieving each motor milestone will be presented for each stage of achievement by timepoint after gene therapy. The number and percentage of subjects achieved each motor milestone for each stage of achievement by time point will be presented. In addition, new milestones observed at a visit that had not been achieved in prior visits for a subject will also be summarized.

Figure will be provided for cumulative milestones achievement by time point. Motor milestones achieved will be listed.

6.2.4. Fine Motor Grasping

Fine motor grasping score is also added as a secondary efficacy variable. Fine motor grasping score is calculated using the total score of the following 6 items from the Grasping section of PDMS-2:

- Item 7: Grasping rattle
- Item 14: Grasping cube
- Item 15: Grasping pellets using raking motion
- Item 16: Manipulating paper
- Item 17: Grasping pellets using thumbs and side of index fingers
- Item 18: Grasping pellets using pad of thumb and pad of index fingers

Summary statistics will be presented for observed score and change from baseline for each item and the total grasping score. Number and percentage of subjects achieved Emerging, Emerging and Mastery, and Mastery for each fine motor grasping item defined above will be summarized by timepoint.

6.2.5. Peabody Developmental Motor Scale, Second Edition (PDMS-2)

PDMS-2 raw scores will be presented for this study. Normally, the raw scores are transformed relative to the subject's age and measured against what is "normal" for that age. If scores are transformed, all the subjects with AADC deficiency would score markedly below their age range because of their development delays. Therefore, no transformation will be performed.

A summary table of descriptive statistics will be presented for the observed scores and change from baseline for each subscale total score and the overall total score by visit.

PDMS-2 raw scores will be presented in a listing for the total score of each subscale performed and the overall total PDMS-2 score.

6.2.6. Bayley-III Assessment

Since Motor Scale has a lot of overlap with PDMS2, only the Cognitive and Language scales from the Bayley-III are used in this study. For convenience, the total of Cognitive and Language scores will be called Total Bayley score.

A summary table of descriptive statistics will be presented for the observed and change from baseline of the total score of Cognitive, Receptive, Expressive, Total Language (sum of Receptive and Expressive), and Total Bayley scores.

A listing of the Bayley-III assessments will be provided.

6.2.7. EQ-5D-Y

The EQ-5D-Y is a comprehensible instrument suitable for evaluating children and adolescents. The EQ-5D-Y descriptive system comprises of the following 5 dimensions: mobility, looking after myself, doing usual activities, having pain or discomfort, feeling worried, sad, or unhappy. The proxy version of the questionnaire will be provided by the site and administered by the caregiver. The caregiver will be asked to rate the child's/adolescent's health-related quality of life in the caregiver's opinion.

The EQ-5D-Y will not be administered for subjects under 4 years of age. If the subject turns 4 during the study, the caregiver will complete the EQ-5D-Y per protocol.

A summary table of descriptive statistics will be presented for the raw “best health rate” score as well as the change from baseline.

A shift table representing a change from baseline for post baseline will be presented for each of the 5 dimensions.

A listing of the responses to each of the 5 dimensions as well as the “best health rate” will be provided for each visit. Change from baseline will be provided for the “best health rate”.

6.2.8. Body Weight

A summary table of descriptive statistics of the observed and change from baseline will be presented. A listing of the weight observed and change from baseline will be provided.

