The SmartFlow MR-compatible ventricular cannula has been used to administer eladocagene exuparvovec in the European Union both commercially and via early access programs and was also used previously to administer a similar viral vector to the putamen of adult subjects to treat Parkinson's disease ([Bankiewicz 2016](#), [Christine 2019](#)). The device will allow precise targeting of the putamen using stereotactic positioning of the cannula through the use of intraoperative magnetic resonance imaging (MRI). Because AADC deficiency is a rare disorder and because the method of administering treatment requires a neurosurgical procedure, a control group in which subjects are administered placebo or undergo a sham procedure will not be used.

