2.2. Secondary Objectives

The secondary study objectives of the study are as follows:

- To assess the PD of eladocagene exuparvovec by evaluation of the following:
 - HVA at Week 48
 - PET at Weeks 8 and 48
 - 5-hydroxyindoleacetic acid [5-HIAA] at Weeks 8 and 48
 - 3-O-methyldopa [3-OMD] at Weeks 8 and 48
- To evaluate the long-term efficacy of eladocagene exuparvovec through Month 60 as assessed by the following:
 - Motor milestone attainment
 - PDMS-2 score
 - Bayley Scale of Infant Development, third edition (Bayley-III)
 - EQ-5D-Y
 - Body weight
 - AADC-specific symptoms
- To evaluate the safety of eladocagene exuparvovec treatment as assessed by treatment-emergent adverse events (TEAEs), neurological examinations, MRI, and clinical laboratory tests.

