4. STUDY POPULATION

4.1. Inclusion Criteria

Subjects will be included if all the following inclusion criteria are fulfilled:

1. Pediatric subjects must have genetically confirmed AADC deficiency with typical clinical characteristics and decreased AADC enzyme activity in plasma.
2. Age range from 1 year to <18 years.
3. Cranium sufficiently developed to allow placement of ClearPoint system for stereotactic surgery.
4. Persistent neurological defects secondary to AADC deficiency despite standard medical therapy (dopamine agonists, monoamine oxidase inhibitor, pyridoxine, or other forms of vitamin B6) in the opinion of the investigator.
5. Unable to ambulate independently (with or without assistive device).
6. Baseline hematology, chemistry, and coagulation values within the normal pediatric laboratory value ranges, unless in the investigator's opinion the out-of-range values are not clinically significant with respect to the subject's suitability for surgery.
7. Subject must test negative for coronavirus disease of 2019 (COVID-19) a maximum of 72 hours prior to receiving gene therapy.

Note: If a subject tests positive for COVID-19 at the Screening or Baseline Visit, he/she will need to have negative test results for 2 weeks (2 weeks since the last positive test result and 2 negative test results a minimum of 14 days apart, with second negative test result no more than 72 hours prior to surgery) before receiving gene therapy. If a COVID-19 test is administered per site policy within 72 hours of the Screening Visit, the results may be used for the AADC-GT-002 study. The COVID-19 test does not need to be repeated after the COVID-19 pre-consent is signed.

8. Subject must be on stable dosage for 3 months prior to baseline for all medications related to treatment of AADC deficiency, including dopamine agonists, monoamine oxidase inhibitors, anticholinergic drugs, and vitamin B6.
9. Females of childbearing potential must have a negative pregnancy test at screening and baseline and agree to abstinence or double-barrier form of contraception for the duration of the study following discharge from the hospital (acceptable methods will be determined by the site).
10. Males sexually active with females of childbearing potential must agree to use a barrier method of birth control during the study following discharge from the hospital.

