7.3.5. Body Weight

Many subjects with AADC deficiency are reported to have feeding/swallowing difficulties and failure to thrive or gain weight as appropriate for growth ([Wassenberg 2017](#)). Therefore, the change in subjects' body weights over time will be assessed as a supportive, exploratory measure of efficacy.

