8.3.3. Analysis of Secondary Endpoints

Observed values and change from baseline in the neurotransmitter CSF metabolites HVA, 5-HIAA, 3-OMD in CSF; brain ¹⁸F-DOPA PET; PDMS-2 total and subscale scores; Bayley-III cognitive and total language subscale scores; EQ-5D-Y scores; body weight; and AADC-specific symptoms will be summarized using descriptive statistics (count, mean, standard deviation, median, minimum, and maximum) or proportion as appropriate for each timepoint.

The number and percentage of subjects who achieve each motor milestone will be summarized by timepoint.

Oculogyric crisis diary data will be summarized by severity, frequency, and proportion and duration of time subjects experienced OGC during the study for selected timepoints, as appropriate.

Respiratory infection rate will be summarized over time.

TEAEs will be summarized as described in Section 8.3.2. The number of subjects who experience dyskinesia, number of dyskinesia episodes, median time to first episode, and summary statistics for duration of dyskinesia events will be provided.

Physical examination, vital signs, MRI, clinical laboratory values, T-cell, anti-AAV2 antibody values, and viral shedding will be summarized by visit, and shift table(s) will be provided if appropriate.

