2.3.2. Secondary Endpoints

The secondary endpoints are as follows:

- Change from baseline in neurotransmitter cerebrospinal fluid (CSF) metabolites HVA (at 48 weeks after administration),
- Change from baseline in PET imaging of putaminal-specific L-6-[¹⁸F] fluoro-3,4-dihydroxyphenylalanine (¹⁸F-DOPA) PET uptake at the end of the Trial Phase (8 weeks after administration) and the Extension Phase (48 weeks after administration).

- Change from baseline in neurotransmitter cerebrospinal fluid (CSF) metabolites 5-HIAA, and 3-OMD at 8 and 48 weeks after administration
- Attainment of motor milestones
- Motor development as assessed by the PDMS-2
- Cognitive and language development as assessed by Bayley-III
- Change in EQ-5D-Y
- Change in body weight
- Assessment of AADC-specific symptoms
- Overall safety profile characterized by type frequency, severity, timing, and relationship to study treatment of any TEAEs, neurological examination findings, brain imaging, or laboratory abnormalities.

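### Body weight is summarised only as raw weight and raw change, so the planned table cannot separate catch-up from ordinary growth or from falling behind

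*SAP*

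**What the plan says.** Both documents list weight among the secondary endpoints; the SAP's entry (section 2.3.2) is "Change in body weight". Weight also belongs to the long-term objective in protocol section 2.2, which opens "To evaluate the long-term efficacy of eladocagene exuparvovec through Month 60 as assessed by the following".

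Protocol section 7.3.5 gives the reason for measuring it: many patients have feeding difficulties and "failure to thrive or gain weight as appropriate for growth". The next sentence limits its role: "body weights over time will be assessed as a supportive, exploratory measure of efficacy".

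The analysis is the same in both documents. Protocol section 8.3.3 includes weight among the variables whose observed values and changes are tabulated: "body weight; and AADC-specific symptoms will be summarized using descriptive statistics". SAP section 6.2.8 says "A summary table of descriptive statistics of the observed and change from baseline will be presented", and adds a listing of the same two quantities. SAP section 7.3 tabulates weight and height again, in the same form, under vital signs. Neither document mentions a z-score, a centile, a growth chart or an expected-growth comparator.

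Three design facts matter. Entry is open to "Age range from 1 year to <18 years" (protocol section 4.1). Follow-up runs to Month 60. Protocol section 1.3 states that "a control group in which subjects are administered placebo or undergo a sham procedure will not be used".

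**The concern.** The reason given for the measure is relative: does a child gain what a child of that age should gain? The planned summary is absolute. Over five years of childhood most children gain weight whatever the treatment does, and a child who is failing to thrive can gain too. With no concurrent control, nothing else in the plan subtracts expected growth.

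Pooling adds a second difficulty. A toddler and an adolescent have different expected gains, so a mean raw change depends on the ages of the children enrolled. With a planned minimum of 3 subjects, one child can move that mean considerably.

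At stake is what a reader can learn from a secondary efficacy endpoint. A positive mean change at Month 60 would be compatible with improvement, with no change in growth status, and with deterioration.

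**Working it through.** The documents state no expected weight change, growth rate or sample-size calculation for this endpoint, so there is no figure to reproduce. The growth rates below are assumptions, shown over a range.

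**Inputs from the documents.** Follow-up is 5 years (Month 60), with intermediate summaries such as Week 8 and Week 48. Entry age is 1 to under 18 years. There is no control group. The analysis is observed value and change from baseline.

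**Step 1. Growth alone, no treatment effect.** Raw change = annual gain × years, with 52.18 weeks to the year.

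| Assumed gain | Week 8 (× 8/52.18) | Week 48 (× 48/52.18) | Month 60 (× 5) |
|---|---|---|---|
| 1 kg/year | +0.2 kg | +0.9 kg | +5 kg |
| 2 kg/year | +0.3 kg | +1.8 kg | +10 kg |
| 3 kg/year | +0.5 kg | +2.8 kg | +15 kg |
| 4 kg/year | +0.6 kg | +3.7 kg | +20 kg |

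The growth component is small at Week 8 and large at Month 60. For a subject near adult size at entry it would be below this range.

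**Step 2. A child who falls behind.** Suppose the child gains a fraction f of an expected G kg/year. Raw change at Month 60 = 5 × f × G, and the shortfall against expected growth = 5 × (1 − f) × G.

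- G = 2, f = 0.5: raw change +5.0 kg, shortfall 5.0 kg.
- G = 3, f = 0.5: raw change +7.5 kg, shortfall 7.5 kg.

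**Step 3. Compare steps 1 and 2.** A child tracking an expected 1 kg/year shows +5 kg. A child gaining half of an expected 2 kg/year also shows +5 kg. A child gaining half of an expected 3 kg/year shows +7.5 kg. The same raw figure can thus describe two different states, and the child who is falling behind can show the larger gain.

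**Step 4. The same children on a growth-referenced scale.** With a z-score for age and sex, a child who tracks the reference has an expected change of 0 at every visit, a child who catches up has a positive change, and a child who falls behind has a negative one. No numerical z-score can be computed here, because the documents name no reference.

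**Step 5. Does anything else in the plan remove growth?** SAP section 4.3.2 allows baseline score and age at gene therapy as covariates where appropriate. No model is specified for weight, and adjusting for age at treatment would not take expected growth out of a within-child change. BMI appears only as a baseline characteristic (SAP section 5.3).

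**The case against.** Several points on the other side are sound.

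- **The SAP does what the protocol asks.** The endpoint is defined as change in body weight, and protocol section 8.3.3 calls for observed values and change. A reader might infer that the SAP departs from its endpoint. It does not: the gap is between the analysis and the reason given for the measure.
- **No claim is attached to a gain.** A reader might infer that the sponsor will count a rise in weight as evidence of efficacy. Neither document says so. The SAP plans one-sample t-tests for HVA and for putaminal PET uptake, and none for weight. It sets no threshold or responder rule, and protocol section 7.3.5 calls the measure supportive and exploratory.
- **The information is not lost.** The listings give each child's weight, height, sex, date of birth and treatment date, so in a very small study a reader could place each child on a growth chart. That stands, but the reader would then choose the reference after seeing the data. What is missing is a prespecified summary.
- **The size varies.** Early visits show little growth and older adolescents have little left, so it would be too strong to say that raw change is positive for every subject.
- **A z-score is not a control.** If untreated children drift down the centiles, a change of 0 could itself be a benefit; if they do not, it means no effect. The documents give no untreated weight course to settle this. The point limits what the z-score can show, but raw change shares the limitation and adds growth to it.

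The decision to keep PDMS-2 scores raw does not carry over. The sponsor gives a reason there, namely that all subjects would score far below their age range. None is given for weight, and change in z-score is informative even from a low starting point.

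**Conclusion.** The point holds as a weakness in the planned summary. Weight was chosen because of poor gain relative to growth, but it will be reported on a scale that cannot show gain relative to growth, in an uncontrolled paediatric cohort followed for five years. Under the assumed 1 to 4 kg/year, growth alone contributes about +5 to +20 kg at Month 60, and less near adult size. Those figures rest on assumed rates. The conclusion that raw change cannot distinguish the three courses needs only that children of different ages have different expected gains.

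The consequence is limited. The measure is descriptive, untested and supportive, so the risk is a misleading reading of one secondary endpoint. There is no inflated error rate and no effect on the primary HVA analysis. The change is worth making because it is cheap and the data are already collected.

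**What to change.** In SAP section 6.2.8, keep the summary of observed weight and raw change, because protocol section 8.3.3 requires it, and add:

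1. The observed value and change from baseline in age- and sex-specific weight-for-age z-score, by visit, with the z-scores also shown in the listing.
2. One growth reference, named before analysis.
3. A stated rule for subjects who pass the reference's upper age limit. Entry at under 18 years plus 60 months allows a subject to be almost 23 at the last visit. One workable rule is to summarise z-scores only at visits within the reference's age range, report the number contributing at each visit, and show raw weight alone after that.
4. A sentence stating that the interpretation of growth rests on the z-score, and that a change of 0 means tracking the reference and neither proves nor excludes a treatment effect.

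SAP section 4.4, which now reports no changes to the protocol's analyses, should record the addition.

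The cost is a few lines of SAP text, one reference table and some programming. Weight is already scheduled, and date of birth and sex are already recorded, so no visit or procedure is added. The drawback is that results will depend on the reference chosen, which is why it should be fixed in advance.

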6.2.9. AADC-Specific Symptoms

The count and percentage of subjects with each symptom will be presented by severity for floppiness, limb dystonia, stimulus-provoked dystonia, muscle tone, spontaneous movement, and muscle power by visit. A listing of AADC-specific symptoms severity and description including floppiness, limb dystonia, stimulus-provoked dystonia, muscle tone, spontaneous movement and muscle power will be provided.

6.2.10. Oculogyric Crisis

Episodes of oculogyric crisis (OGC) will be captured through paper or eDiary with specified questions.

Data from OGC diaries will be summarized in 2 ways:

1. Proportion of time and hours of OGC experienced per month
2. Frequency of OGC per month

The proportion of time for each subject will be calculated as total duration of all OGC episodes within the defined interval divided by total hours of that interval. Figures will be provided for the proportion of time and for the frequency of OGC per month.

If a subject did not have full month's record for a month at the beginning period prior to gene therapy or did not have full month's records for a month toward the end of the series of the

timepoints after gene therapy, the actual first date of reporting OGC in the diary (for prior treatment records) or the last date of reporting OGC in the diary (after treatment) for that month will be used to calculate total hours reporting OGC for that time period for that subject.

A listing of OGC data will be presented and will include start date and time, stop date and time, duration, medications taken, as well as pre-specified symptoms including uncontrolled eye movement, still limbs, lock jaw, neck dystonia, tongue thrust, trunk dystonia and overall assessment of severity.

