Abbreviations: 3-OMD, 3-O-methyldopa; 5-HIAA, 5-hydroxyindoleacetic acid; ¹⁸F-DOPA, fluoro-3,4-dihydroxyphenylalanine; AADC, aromatic L-amino acid decarboxylase (deficiency); AAV2, adeno-associated virus, serotype 2; AE, adverse event; aPTT, activated partial thromboplastin time; BL, Baseline; Bayley-III, Bayley Scale of Infant Development, third edition; CBC, complete blood count; CMP, comprehensive metabolic panel; COVID-19, coronavirus disease of 2019; CSF, cerebrospinal fluid; CT, computed tomography; D, day; diff, differential count; Disc, discharge; ECG, electrocardiogram; eDiary, electronic diary; HVA, homovanillic acid; ICU, intensive care unit; IgG, immunoglobulin G; INR, international normalized ratio; L-DOPA, L-3,4-dihydroxyphenylalanine; MHPG, 3-methoxy-4-hydroxyphenylglycol; MRI, magnetic resonance imaging; OGC, oculogyric crisis; PDMS-2, Peabody Developmental Motor Scale, second edition; PET, positron emission tomography; PI, principal investigator; PT, prothrombin time; PTT, partial thromboplastin time; RBC, red blood cell (count); T1-MPRAGE, T-1 weighted magnetization prepared rapid gradient echo; T2-FLAIR, T2-weighted fluid-attenuated inversion recovery; W, week; WBC, white blood cell (count)

^a Any study visit may take place over a 3-day period, as necessary.

^b Screening will be conducted and completed up to 9 weeks prior to the Baseline Visit. Subjects who are unable to adhere to the Screening Visit window specified in the protocol due to unforeseen circumstances (eg, COVID-19) may be rescreened upon sponsor approval. If the Baseline Visit does not occur within 9 weeks after the Screening Visit per the Screening Window, the only Screening Visit assessments that need to be performed again are the local laboratory assessments, physical exam, and vital signs.

^c Surgical procedure will require a minimum of 1 night in the ICU and hospitalization for up to 3 days. Subjects will be required to stay in the vicinity of the study clinic for a minimum of 7 days total post procedure.

^d If historic AADC diagnosis clinical testing results are available, they may be used to determine eligibility. If historic AADC diagnosis clinical testing results are used to determine eligibility, AADC diagnosis clinical testing does not need to be repeated at Screening.

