^p Complete physical examination at Screening, Baseline Visit, and on Dosing Day (D1), and targeted physical examination for all other visits. The complete physical examination will consist of an examination of the following: neurological assessment and assessments of general appearance, any changes to feeding tube placement or removal, skin, head, eyes, ears, nose, throat, neck (including thyroid), lymph nodes, chest, heart, abdomen, and extremities. The targeted physical examination will consist of a neurological assessment, general appearance assessment, any changes to feeding tube placement or removal, and heart auscultation.

^q Vital signs include temperature, pulse, respiratory rate, and blood pressure.

^r Brain MRI with gadolinium performed at Screening to exclude subjects who may have pre-existing conditions.

^s Brain MRI with gadolinium to check for persistent CSF leakage/fistula and inflammatory changes (eg, aseptic ventriculitis/meningitis). An MRI should be performed immediately if a CSF leak is suspected.

^t Brain CT for postdose hemorrhage check should be performed within 6 hours after the end of surgery.

^u PET scans will be centrally read.

^v P-A and lateral chest x-ray.

^w Parent/caregiver must complete eDiary or paper diary for each OGC occurrence throughout the Trial Phase and Extension Phase. In the event that the eDiary cannot be used, a paper version will be provided.

^x Findings for AADC-specific symptoms will be collected at every in-person visit after D1. These assess for floppiness (hypotonia), limb and stimulus-provoked dystonia, and muscle power.

^y Laboratory tests (PT; PTT or aPTT; INR; CBC w/diff; and CMP analysis [including total bilirubin]). These will be assessed by a local laboratory.

^z The EQ-5D-Y will not be administered to subjects under 4 years of age. If the subject turns 4 during the study, the caregiver will complete the EQ-5D-Y per protocol after the subject turns 4.

Table 2: Schedule of Events for Extension Phase

Visit	10	11	12	13	14	15	16	17	18	19	20
Type of Visit (In-Person or Phone)	Phone	In-Person	Phone	Phone	In-Person	Phone	Phone	In-Person	Phone	Phone	In-Person
Visit Window ^a	W10 ±2D	W12 ±3D	W16 ±2D	W20 ±2D	W24 ±3D	W28 ±2D	W32 ±2D	W36 ±3D	W40 ±2D	W44 ±2D	W48/ET ^b ±3D
Pregnancy Test ^c		X			X			X			X
CSF neurotransmitter analysis ^{d,e,f}											X
Anti-AAV2 antibody (IgG and neutralizing titers) ^d		X			X			X			X
Viral shedding (blood and urine) ^{d,g}	X			X			X				X

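### The SAP states no scaling for OGC frequency or hours in partial months and does not define the month, so a short baseline or last month can mislead

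*SAP*

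**What the plan says.** SAP 6.2.10 gives two summaries of the diary data: "Proportion of time and hours of OGC experienced per month" and "Frequency of OGC per month". Only the proportion has a formula: "total duration of all OGC episodes within the defined interval divided by total hours of that interval". Both are plotted: "Figures will be provided for the proportion of time and for the frequency of OGC per month".

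For a month without full records at the start of the pre-treatment series or the end of the post-treatment series, the SAP takes "the actual first date of reporting OGC in the diary (for prior treatment records) or the last date of reporting OGC in the diary", and that date "will be used to calculate total hours reporting OGC for that time period for that subject". Frequency is not mentioned in this rule. The SAP does not say how many days a month has.

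The diary is event-driven: "Parent/caregiver must complete eDiary or paper diary for each OGC occurrence throughout the Trial Phase and Extension Phase" (Protocol 7.1, Table 1, footnote w). Instructions for its use are given at Screening, Week -10 to Week -2. Protocol 8.3.3 names the OGC summaries but adds no rule for incomplete months.

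The next SAP section, 6.2.11, handles a similar quantity differently: respiratory infection episodes are divided by the subjects' time in the study.

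**The concern.** A count per month is comparable across months only if each month is observed for the same time or the count is divided by the time observed. Here unequal months are part of the design. The pre-treatment record depends on when the child was screened, the post-treatment record stops at Week 48, and withdrawal can cut it at any point.

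If the counts are left as they fall, the two ends of the series err in opposite directions. A short pre-treatment month lowers the baseline and hides benefit. A short last month looks like a late improvement and exaggerates benefit. The size differs between children, and with a planned minimum of 3 subjects one child can move a plotted mean. No test of OGC is planned, so the summary and the figure are the evidence on this symptom.

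**Working it through.** The plan gives no figure to reproduce. The check is arithmetic at a constant OGC rate, with no true change.

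**Inputs from the documents**
- Pre-treatment diary: about 14 to 70 days. Screening falls in Week -10 to Week -2. Table 1, footnote b agrees on the upper end: "Screening will be conducted and completed up to 9 weeks prior to the Baseline Visit", and Baseline is Week -1, so (9 + 1) × 7 = 70 days.
- Post-treatment diary: to the end of the Extension Phase, 48 × 7 = 336 days, visit window ±3 days.

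**Assumptions, not in the documents**
- The month is 28, 30 or 30.44 days (365.25/12 = 30.4375).
- The diary is kept from the Screening visit onward.

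**Formula.** Unscaled count ÷ true monthly count = days observed ÷ month length.

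**Pre-treatment partial month**

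| Diary before dosing | 28-day month | 30-day month | 30.44-day month |
|---|---|---|---|
| 14 days | 14/28 = 0.50 | 14/30 = 0.47 | 14/30.44 = 0.46 |
| 42 days (remainder) | 14/28 = 0.50 | 12/30 = 0.40 | 11.56/30.44 = 0.38 |
| 70 days (remainder) | 14/28 = 0.50 | 10/30 = 0.33 | 9.12/30.44 = 0.30 |

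The partial month is understated by about 50% to 70%. With 42 or 70 days there are also one or two full pre-treatment months. With 14 days the partial month is the only one, and an unchanged full 30-day month after dosing would look like a rise of 30/14 − 1 = 114%.

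**Last month, by day on which the diary ends**

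| Last day | 28-day month | 30-day month | 30.44-day month |
|---|---|---|---|
| 333 | 25 days left, 0.89 | 3 left, 0.10 | 28.62 left, 0.94 |
| 336 | none (12 × 28) | 6 left, 0.20 | 1.19 left, 0.04 |
| 339 | 3 left, 0.11 | 9 left, 0.30 | 4.19 left, 0.14 |

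At day 336 the apparent fall is nil, 1 − 0.20 = 80%, or 1 − 0.04 = 96%. The visit window alone moves the 30.44-day case from a 6% to a 96% fall.

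**Can the existing partial-month rule be borrowed?** Its boundary is a date on which an OGC was reported, so OGC-free days at the edge of the record drop out of the denominator. A simulation with Poisson episodes of fixed length (200,000 draws, partial months with at least one episode) gave these mean ratios of the resulting proportion to the true one:
- 12 episodes per 30 days, 6 days observed: 1.55
- 12 episodes per 30 days, 14 days observed: 1.19
- 4 episodes per 30 days, 6 days observed: 3.48

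In the last case 45% of partial months had no episode, and the boundary is then undefined. Dividing by days observed gave 1.00 throughout.

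**Check of the remedy** (30-day month, 12 episodes per month). Six days give 12 × 6/30 = 2.4 episodes, and 2.4 × 30/6 = 12. Fourteen days give 12 × 14/30 = 5.6, and 5.6 × 30/14 = 12. Hours scale by the same factors.

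**The case against.** The strongest reply is that the SAP is silent. It never says that raw counts will be used, a frequency per month can be read as a rate, and the table and figure shells are in a separate document (SAP section 8). This stands in part. A reader might infer that the SAP prescribes unscaled counts, and the text does not go that far. But an explicit partial-month rule that serves only total hours, next to an infection rate with a written denominator, makes the unscaled count the plain reading. Two programmers could produce different figures.

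A reader might also infer that the proportion of time is already scaled to the days observed and is the model to copy. It is not, because its boundary is an OGC report date.

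The partial-month sentence could be meant to cover hours of OGC too, since hours and proportion are one listed item. That would not help: every episode lies within the first and last report dates, so bounding by them leaves the hours total unchanged.

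The consequences are limited. Protocol 8.3.3 confines the summaries to selected timepoints as appropriate, so short months could be left out. Episodes are listed with start and stop times, so rates can be recalculated. It would be too strong to say that the before-after comparison cannot be read: only edge months are affected, and a completer keeps at least ten full months after dosing.

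**Conclusion.** The point holds as a gap in SAP 6.2.10 with a predictable distortion if the text is followed plainly. The baseline effect is the firmer part: a 14-day pre-treatment record shows 46% to 50% of the true monthly count under all three month lengths.

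The last-month effect is conditional. A reader might take an 80% fall as the expected result, but that needs a 30-day month and a diary ending on day 336. With 28-day months and a visit on exactly that day, completers have no short last month. Early withdrawal can produce any fraction.

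These sizes assume a constant OGC rate and a diary begun at Screening. OGC belongs to a descriptive secondary endpoint, so the primary analysis is untouched. Label: cheap improvement.

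**What to change.** In SAP 6.2.10:

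1. Define the month as a fixed number of days counted from dosing. For example, 28 days fits the visit schedule, which has a contact at every fourth week to Week 48.
2. For every interval, full or partial, report frequency and hours as (episodes or hours ÷ days in the observation window) × month length.
3. Set the window by diary start (Screening), dosing, and Week 48 or withdrawal, not by the first or last OGC report. An event-driven diary cannot distinguish an OGC-free day from an unrecorded one, so the window has to come from these dates.
4. Use the same window for the proportion of time.
5. Do not plot intervals below a stated minimum, for example 7 observed days.

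The cost is a few sentences and one denominator in the program. The downside is noisier rates in short intervals: with a 28-day month, one episode more or less moves the rate by 28/14 = 2 in a 14-day interval and by 28/7 = 4 in a 7-day interval.
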